	Potentially influential factors will be considered and addressed with a linear regression model. This model may include covariates such as age, sex, NVIQ or NVIQ equivalent, genotype, history of regression (yes/no), ASD diagnosis yes/no with no more than two covariates included in any model. Descriptive statistics and corresponding graphics will be used to present the results. The efficacy analysis details will be specified in the SAP.	
	Pharmacokinetics: NNZ-2591 PK concentrations will be listed by subject and time point for each dose level with actual time they were acquired. The concentrations will be summarized by time, dose level and age group. For the concentrations measured at trough points dose relationship will be examined statistically with age group and/or body weight of patient as covariate.	
	Overall exposure parameters for NNZ-2591 such as C_{max} and AUC _{tau} may be derived by sparse non-compartmental analysis (NCA). Additionally, PK concentrations of NNZ-2591 measured in pediatric patients will be used to refine a population PK model developed from adult NNZ-2591 PK data and extrapolated to the pediatric population. After refinement, complete profiles for each patient will be simulated using range of variability of model parameters and individual covariate effects. A standard NCA approach will be used for simulated profiles to calculate parameters C_{max} , AUC _{tau} , etc. for characterization of NNZ-2591 exposure in pediatric patients.	
	The PK analysis details will be specified in the PK Statistical Analysis Plan (PK SAP).	

Protocol Neu-2591-P	MS-001: Pediatric Safety, Tolerability, and Pharmacokinetic Study
	Biomarkers and Microbiome: Biomarker analysis will be detailed in a separate analysis plan and will not include DNA sequencing.
	Microbiome analysis will be described in a separate analysis plan.
Trial Sites	Approximately 4 to 7 sites in the US.

Neuren Pharmaceuticals Ltd.	Clinical Trial Protocol	Version 3.0
Confidential	Neu-2591-PMS-001	October 30, 2023

4. SCHEDULE OF ASSESSMENTS

Table 1 Schedule of Assessments for Neu-2591-PMS

Paviad	Screen Baselin	ing/ 1e ^a	Baseline	aseline Treatment Period												Follow- up ^b	
renou	4 10 0 1	Vicit 1	0	1	2	2	4	5	6	7	0	0	10	11	12	13/FOT	15
Visit Week	6	+2 wks	U	1	-	3	*	2	U	ľ	•	9	10		12	15/201	15
Visit Number	1	2	3	4	5	6	7	8	9	10	11	12	13	14	15	16	17
Visit window (days)	±2ª	±lª	±2ª,¢	±l	±2	±1	±1	±l	±2	±l	±1	±1	±l	±l	±1	-3	+4
Type of Visit	Clinic ^d	Remote and In- Home ^{e,1}	Clinic ^d	Remote and In- Home e,f	Clinic ^d	In- Home ^f	Remote and In- Home ^{e,f}	In- home ^f	Clinic ^d	In- Home ^f	Remote and In- Home ^{e,f}	In- Home ^f	Remote and In- Home ^{e,f}	In- Home ^f	In- home ^f	Clinic ^d	Remote and In- Home ^{e,f}
Informed consent (mandatory)	x																
Consent for reuse of leftover Biomarker and PK samples (optional)	x																
Inclusion/exclusion criteria	x		x														
Medical history	X	X	х												· · · · ·		
Confirm documented PMS diagnosis and genotype	x																
PMS history and exam	X																
Confirm comorbid psychiatric disorders by DSM-5	x																
Rapid SARS-CoV-2 test	X		Х			0	[]]				1					Х	
Autism Mental Status Exam	x																
Recent clinical history				X	х		X		Х		X	l l	X			Х	X
Physical examination ^g	X		Х		Х		Xh		Х		Xh		Xh			X	X ^h
Targeted Physical Exam ^g		N		Ν	-	N	N	N		N	N	N	Ν	N	N		N
Neurological examination	x		x		х		Xh		х		Xh		X ^h			x	X ^h

Page 28 of 117

Neuren Pharmaceuticals Ltd. Confidential				Clinical Trial ProtocolVersion 3.0Neu-2591-PMS-001October 30, 2023													
	Screen Baselin	ing/ ne ^a	Baseline	Treatm	ent Peri	iod											Follow- up ^b
Period	4 to 6	veeks						1-		-	-	-		1	1		
	-4 to -	Visit 1	0	1	2	3	4	5	6	7	8	9	10	11	12	13/EOT°	15
Visit Week	0	+2 wks			-	-	-		0	10		10	10	14	1.0	16	
Visit Number	1	2	3	4	5	0	/	8	9	10	11	12	13	14	15	10	17
Visit window (days)	±2ª	±1,	±24,0	1 +1	±2	±1	±	브	±2	±1	±1	±	±1	±1	±	-3	+4
Type of Visit	Clinic	Remote and In- Home ^{e,i}	f	Remote and In- Home e,f	Clinic	In- Home ^f	Remote and In- Home ^{e,f}	In- home ^f	Clinic	In- Home ^f	Remote and In- Home ^{e,f}	In- Home ¹	Remote and In- Home ^{e,f}	In- Home ^f	In- home ^f	Clinic ^a	Remote and In- Home ^{e,f}
														_			
Vital signs	x	N	x	N	x	N	N	N	x	N	N	N	N	N	N	x	N
Height/length	x	-	x	-							-				 	x	
Weight	x	N	x	N	x	N	N	N	x	N	N	N	N	N	N	x	N
Review for AEs/SAEs		-		XN	x	N	XN	N	x	N	XN	N	XN	N	N	x	XN
Caregiver Diaryk	x	х	x	X, N	x	N	x	N	x	N	x	N	x	N	N	x	X, N
IMP administration ^c			x							Twice da	aily			L	-		 
Review dosing compliance documentation in diary ¹				X, N	x	N	X, N	N	x	N	X, N	N	X, N	N	N	x	
12-lead ECG	X		X		X				х							X	N
CBC with differential	X		Х		X		N		Х		N		N			Х	N
Coagulation ^m	X		Х		Х		N		Х		N		N			X	N
Comprehensive metabolic panel ⁿ	x		х	N	x	N	N	N	х	N	N	N	N	N	N	x	N
Urinalysis ^o	X		X	N	X	N	N	N	Х	N	N	N	N	N	N	X	N
Urine screen for drugs of abuse ^o	x								·								
TSH, Free T3, Free T4	x															x	 
HbA1c	x															x	
Serum pregnancy test ^p	x						2		X					1		X	
Blood samples for PK ^q					X				X							X	
Blood sample for biomarkers ^r	X		x													x	

Page 29 of 117

Neuren Pharmaceuticals I	.td.		Clinic	al Trial I	Protocol					Vers	sion 3.0						
Confidential			Neu	-2591-PN	IS-001				0	ctober 3	0, 2023						_
Period	Screening/ Baseline ^a		Baseline	Baseline Treatment Period													Follow- up ^b
	-4 to -	Visit 1	0	1	2	3	4	5	6	7	8	9	10	11	12	13/EOT	15
Visit Week	6	+2 wks															
Visit Number	1	2	3	4	5	6	7	8	9	10	11	12	13	14	15	16	17
Visit window (days)	±2ª	±1ª	±2ª,c	±1	±2	±1	±1	±1	±2	±1	±1	±1	±1	±1	±1	-3	+4
Type of Visit	Clinic	Remote and In- Home ^{e,i}	Clinic ^d	Remote and In- Home e,f	Clinic ^d	In- Home ^f	Remote and In- Home ^{e,f}	In- home ^t	Clinic ^d	In- Home ^f	Remote and In- Home ^{e,f}	In- Home ^f	Remote and In- Home ^{e,f}	In- Home ^f	In- home ^t	Clinic ^d	Remote and In- Home ^{e,f}
Stool sample for microbiome	x		х													х	
CGI-I						0			Х							X	Х
CGI-S	Х		Х						х							X	х
	1																
Stanford-Binet Intelligence Scales version 5 (SB5) or Mullen Scales of Early Learning ^r	x															x	
MB-CDI			X													X	
ORCA			Х													X	
Caregiver Top 3 Concerns	x	x	х						x							x	x
ABC-2	X	X	х						x							X	x
BPI-SF	5		X		-											X	
Caregiver Global Impression-Change																x	
OI-Disability			X													X	
ICND-Overall quality of life rating			х				2				· · · · · · · ·					х	
CSHQ	X	X	X						x			1				X	x
Vineland Adaptive Behavior Scales-3			х													x	
GIHO	X	x	x				· · · · ·		x							X	x
Study Exit Form		1			0	0 0	0		1								X ^s

Page 30 of 117

Neuren Pharmaceuticals Ltd.	Clinical Trial Protocol	Version 3.0
Confidential	Neu-2591-PMS-001	October 30, 2023

X = Conducted by site personnel or caregiver as applicable

N = Conducted by visiting nurse

Abbreviations: ABC-2=Aberrant Behavior Checklist-2; AE=adverse event; BPI-SF=Behavior Problems Inventory-Short Form; CBC=Complete Blood Count; CGI-I=Clinical Global Impression Scale-Improvement; CGI-S=Clinical Global Impression Scale-Severity; CMP=Comprehensive Metabolic Panel; CSHQ=Child Sleep Habits Questionnaire; DSM-5=Diagnostic and Statistical Manual of Mental Disorders, Fifth Edition; ECG = electrocardiogram; EOT=end of treatment; GIHQ=GI Health Questionnaire; ICND=Impact of Childhood Neurological Disability; IMP=Investigational Medicinal Product; MB-CDI=MacArthur-Bates Communicative Development Inventory; ORCA=Observer-Reported Communication Assessment; PK = pharmacokinetic; PMS=Phelan-McDermid syndrome; PMS-DSRS=PMS Clinician Domain Specific Rating Scale; QI-Disability=Quality of Life Inventory- Disability; SAE=serious adverse events; Stanford Binet Intelligence Scales ver 5; T3 = triiodothyronine; T4 = thyroxine; TSH = thyroid stimulating hormone.

^a No assessments can be conducted until after informed consent has been given by the caregiver or legally authorized representative. Training for the caregivers on all caregiver completed assessments must be done before the caregiver/rater may complete the assessments. The Screening/Baseline period will be conducted over 4 to 6 weeks. The second visit during the Screening/Baseline period (Visit 2) should be conducted 2 weeks ± 1 day after the Screening visit (Visit 1). The subject will then remain in Screening for an additional 2 to 4 weeks. The caregiver diary must be completed daily during the entire Screening/Baseline period whether it is 4 weeks or 6 weeks. The Screening visit (Visit 1) and Baseline visit (Visit 3) may be conducted over three consecutive days. It is preferrable that ECGs, safety labs and biomarker sample collection are conducted on the same day. All assessments must be completed within the window for the visit (visit day ± 2 days). For Visit 3, all assessments must be completed before administration of the IMP.

^b The End of Treatment visit is conducted when the subject is still on IMP treatment. For early termination, in addition to study completers, subjects who have received IMP for longer than 2 weeks and discontinue prematurely any time after Visit 5 should return to the investigational site for final safety and efficacy assessments as scheduled for the EOT visit (Visit 16) and complete the study exit form.

^e At Visit 3, the first dose of IMP will be administered in the clinic after all Baseline assessments are completed, or, if the Investigator judges that it is too late in the day, on the following day. The subject should be monitored for at least three hours post first dose. If the first dose is administered the day following Baseline, vital signs (except height) should be collected before the dose is administered. Day 1 of dosing is defined by the date when the first dose is taken. At the Baseline visit, the site will dispense an adequate supply of IMP for dispensing by the caregiver at home. Dosing at the end of Baseline counts as Day 1 whether one or two doses are given. Dosing may not exceed 91 days including Day 1, and all efficacy assessments for the EOT visit must be completed on or before Day 91 of treatment.

^d A clinic visit is preferred but an off-site visit may be conducted for a scheduled in-clinic visit in extenuating circumstances due to the COVID-19 health crisis. All requests for off-site visit assessments due to extenuating circumstances must be approved in advance by the Sponsor or Medical Monitor. The in-clinic visits may be conducted over three consecutive days. All assessments including caregiver-completed assessments must be done within the window for the visit.

Neuren Pharmaceuticals Ltd.	Clinical Trial Protocol	Version 3.0
onfidential	Neu-2591-PMS-001	October 30, 2023

^e This is a combined remote and in-person nurse visit. The remote visit is conducted by the site via telemedicine or video facilities as appropriate. Any caregiver-completed assessments should be completed the same day of the visit or no earlier than the day before the visit (except the Caregiver Diary which is completed daily) and reviewed by the Investigator. A modified version of the physical and neurological exam will be done at the remote visits based on the guidance document provided to the Investigator. At Week 4, the site should confirm with the caregiver that the child has started the new dose if they were approved for dose titration. These combination remote/in-home visits will be conducted simultaneously whenever possible, or they will ideally be conducted on the same day. If that is not possible, the telemedicine visit and the nurse visit may be conducted over two consecutive days. If that is not possible, the telemedicine visit and the nurse visit may be conducted once two consecutive days. A combined remote visit may be conducted in-clinic by the study staff if agreed upon by the Investigator and the caregiver. See Section 9.1 and Section 9.2.

^f In-home visits will be conducted by a visiting nurse. At every nurse visit, the nurse will collect urine, vital signs including weight, and blood samples for a comprehensive metabolic panel (CMP). The nurse will also conduct a targeted physical exam assessing general appearance, abdominal/CVA tenderness, and edema. A suprapubic exam (bladder palpation) to assess for urinary retention may be performed. The visiting nurse will also review the dosing diary, query oral intake, and do a review of tolerability. Blood samples for CBC with differential and coagulation will be collected at Weeks 4, 8, 10 and Week 15 (indicated by "N" in the Schedule of Assessments). At the post-treatment follow-up visit at Week 15, the visiting nurse will also collect ECG, in addition to the above assessments. At Week 7, the site will also have a phone call with the caregiver to confirm that the child has started the new dose if they were approved for dose titration. The site will confirm the visiting nurse has been informed so the dosing schedule can be reviewed with the family during the in-home visit. A nurse-only in-home visit may be conducted in-clinic by the study staff if agreed upon by the Investigator and the caregiver. See Section 9.1 and Section 9.2.

^g The in-clinic physical exam will include an abdominal exam and an assessment of CVA. A suprapubic exam (bladder palpation) to assess for urinary retention may be performed. General awareness will be captured as part of the neurological exam. For in-home nursing visits, the nurse will do a Targeted Physical exam assessing general appearance (e.g., alertness), an abdominal/CVA, and edema. A suprapubic exam (bladder palpation) to assess for urinary retention may be performed.

^h A modified version of the neurological and physical exam will be done for the remote visit based on the guidance document provided to the Investigator.

^j The visiting nurse will query any changes in tolerability during the in-home visit. Any changes will be noted and provided to the Investigator. The Investigator will also query changes in tolerability and note any changes in the remote assessment. The Investigator is responsible for determining and reporting any changes that qualify as Adverse Events.

^k The caregiver fills out the diary daily from the first day of screening through two weeks after the EOT Visit. X denotes review of the Caregiver Diary including the daily summary log, medication log, non-medicinal treatments log, seizure log and new/changes in symptoms log. All visits:

Neuren Pharmaceuticals Ltd.	Clinical Trial Protocol	Version 3.0
Confidential	Neu-2591-PMS-001	October 30, 2023

The Investigator (or appropriately credentialed designee) is responsible for reviewing for ALL visits. In-home visits: At the in-home nurse visit, the nurse will review the Caregiver Diary to flag and check any issues that could be reported as AEs. The nurse will notify the site about any urgent issues the day of the visit and note anything else in the source documents. The nurse does not sign the diary. The source documents and the diary will be sent to the site. The Investigator (or appropriately credentialed designee) will review the diary and source documents collected at the in-home visit.

Note: There are two rows for Caregiver Diary review procedures (to emphasize the importance of thorough and complete dosing documentation): this row (Caregiver Diary) denotes that the caregiver fills out the diary daily and a designated clinician reviews it for safety/tolerability; a second row (Review dosing compliance documentation in diary, see footnote "l") is intended to ensure that the caregiver is administering IMP/documenting dose properly in the Caregiver Diary.

¹ The daily dosing log in the Caregiver Diary will be reviewed at all post-baseline visits through EOT. If any doses are missed or mis-dosed, this should be queried with the caregiver and appropriate feedback given to the family. This feedback should be documented in the source documents. At the in-home nurse visit, the nurse will review the caregiver diary to check any issues and provide feedback to the family at the visit. The nurse will notify the site about any urgent issues the day of the visit and note anything else in the source documents. The nurse does not sign the daily dosing log/summary page. The source documents and the diary will be sent to the site. The Investigator (or appropriately credentialed delegee) will review the diary and source documents collected at the in-home visit.

^m Coagulation includes prothrombin time, activated partial thromboplastin (aPTT), and international normalized ratio (INR).

ⁿ A Comprehensive Metabolic Panel will be assessed every post-enrollment visit (see Section 9.5.2). If abnormal findings are observed on renal or liver function tests, additional tests as is clinically indicated may be conducted as described in Sections 9.5.2.1 and 9.5.2.3).

^oBoth urinalysis and a urine screen for drugs of abuse will be evaluated at Screening (See Section 9.5.2).

^p For female subjects who have reached menarche.

^q See Table 2 and Table 3 for PK blood collection times.

^r The Mullen is done for subjects who cannot obtain basal on SB5 or for whom the SB5 is developmentally inappropriate.

^s The study exit form should also be completed if the subject terminates the study early.

Table 2 Pharmacokinetic Blood Sampling Schedule (Subjects Ages 7 to 12 Years Old)

Week	Visit No.	Treatment	Timing of Sample (relative to start of dosing) ^a	Sample Time Point
2	5		Pre dose (-120 to -15 minutes) ^b	1
			1-3 hours post dose ^c	2
			4-7 hours post dose ^c	3
6	9	Mid-treatment	Pre dose (-120 to -15 minutes) ^b	4
			1-3 hours post dose ^c	5
			4-7 hours post dose ^c	6
13	16	End of Treatment	Pre dose (-120 to -15 minutes) ^b	7
			1-3 hours post dose ^c	8
			4-7 hours post dose ^c	9

^a All post-dose windows are determined from the first dose of the visit (morning dose) and all PK samples must be collected before the second dose (PM dose).

^b Pre dose counts as both T0 and 12 hours post dose from previous evening (near trough). The previous evening's dose should be taken in the evening as late as possible, preferably before bedtime.

^c Post-dose sample collection can be +/- 15 minutes of the target time and must be at least 30 minutes from the previous sample (samples can be no closer than 30 minutes apart). The actual collection time must be recorded.

Week	Visit No.	Treatment	Collection Window	Timing of Sample (relative to start of dosing) ^a	Sample Time Point	Comment	
2	5			Pre dose (-120 to -15 minutes) ^b	1		
			A	1-3 hour post dose ^c	2	Sample 2 can be taken at	
			OR	OR		either collection window A or B ^d	
			В	4-7 hours post dose ^c			
6	9	Mid-treatment		Pre dose (-120 to -15 minutes) ^b	3		
			Α	1-3 hours post dose ^c	4	Sample 4 can be taken at	
			OR	OR		either collection window A or B ^d	
			В	4-7 hours post dose ^e			
13	16	End of Treatment		Pre dose (-120 to -15 minutes) ^b	5		
		A 1-3 hours post dose ^c		6	Sample 6 can be taken at		
			OR	OR		either collection window A or B ^d	
			В	4-7 hours post dose ^c			

Table 3 Pharmacokinetic Blood Sampling Schedule (Subjects Ages 3 to <7 Years Old)	^a All post-dose windows are determined from the first dose of the visit (morning dose) and all PK samples must be collected before the second dose (PM dose).

^b Pre dose counts as both T0 and 12 hours post dose from previous evening (near trough). The previous evening's dose should be taken in the evening as late as possible, preferably before bedtime.

^c Post-dose sample collection can be +/- 15 minutes of the target time and must be at least 30 minutes from the previous sample (samples can be no closer than 30 minutes apart). The actual collection time must be recorded.

^d For the 3 to <7 year-old age range, two sampling timepoints are taken at each visit. The post-dose sample may be taken at either collection window A or collection window B. Ideally, it is better that the second sample is not taken at the same collection window at each visit. So, an attempt should be made to vary the collection time of the second sample as is feasible. For example, if on visit 5 the second sample is taken in collection window B, at visit 9 or 16, the second sample should ideally be taken in collection window A.

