Dosing Schedule Week 1 Week 3 Week 4 Week 6 Week 7 Week 9 Week and and 10 to and Week 2 Week 5 Week 8 Week 13 4 mg/kg 4 mg/kg 8 mg/kg 8 mg/kg BID 12 12 mg/kg 12 mg/kg BID BID BID mg/kg BID (16 mg/kg (8 mg/kg (8 mg/kg (16 daily)1 BID (24 mg/kg BID daily) daily)1 mg/kg (24 daily) (24 daily) mg/kg mg/kg daily) daily) DSMC DSMC DSMC Reviews Reviews reviews data after **Data Prior Data Prior** to 2 weeks to Uptitration² Uptitration² on 12 mg/kg to confirm safetv² BID = twice daily; DSMC = Data Safety Monitoring Committee ¹Subjects will stay on their current dose until the data is reviewed by the DSMC. ²Expected time for DSMC review will be one week. The dose titration schedule may be modified based on updated pharmacokinetic modelling analyses that include data from the study. The IMP will be administered at a starting dose of 4 mg/kg BID for a total of approximately three weeks. After two weeks of dosing at the starting dose, the data will be reviewed by the DSMC, and the subjects will stay on the starting dose while the data are reviewed. If safety and tolerability are deemed acceptable, subjects will be uptitrated to 8 mg/kg BID and be dosed for a total of approximately three additional weeks. After two weeks of dosing at 8 mg/kg, the data will be reviewed by the DSMC, and the subjects will stay on the 8 mg/kg dose while the data are reviewed. If safety and tolerability are deemed acceptable, subjects will be up-titrated to12 mg/kg BID and remain on this dose for seven weeks. The DSMC will determine if dose escalation can proceed based on pre-specified stopping rules detailed in the body of the protocol. The total administration period for NNZ-2591 will be 13 weeks. For staggered enrollment, the subjects will be divided into three groups by age: 9 to 12-year-olds (Group 1), 6 to 8-year-olds (Group 2), and 3 to 5-year-olds (Group 3). The DSMC will also review and approve the start of enrollment in the younger age groups.

NNZ-2591 is provided as a ready-to-use strawberry flavored liquid for oral administration. The IMP should not be mixed with water, liquid thickeners, or food for administration. The dose can be taken from a cup or dosing syringe. Doses should be given on an empty stomach (2 hours after the previous meal or snack and 30 minutes prior to the next).

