11.5 Pharmacokinetic Analysis

The PK analysis will be based on the endpoints listed in Section 6.3.1. Pharmacokinetic (PK) measures will be collected from all subjects at Visits 5 (Week 2), 9 (Week 6,) and 16 (Week 13, EOT).

NNZ-2591 PK concentrations will be listed by subject and time point for each dose level with actual time they were acquired. The concentrations will be summarized by time, dose level, and age group. For the concentrations measured at trough points dose relationship will be examined statistically with age group and/or body weight of subject as covariate.

Overall exposure parameters for NNZ-2591 such as C_{max} and AUC_{tau} may be derived by sparse noncompartmental analysis (NCA). Additionally, PK concentrations of NNZ-2591 measured in pediatric subjects will be used to refine a population PK model developed from adult NNZ-2591 PK data and extrapolated to pediatric population. After refinement, complete profiles for each subject will be simulated using range of variability of model parameters and individual covariate effects. A standard NCA approach will be used for simulated profiles to calculate parameters C_{max} , AUC_{tau}, etc. for characterization of NNZ-2591 exposure in pediatric subjects.

The PK analysis details will be specified in the PK SAP.

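### For children aged 3 to <7 the site chooses the single post-dose PK window, and nothing balances early and late samples across children at a dose level

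*Protocol*

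**What the plan says.** Protocol Section 4 sets two PK sampling schedules. Table 2 (ages 7 to 12) takes a pre-dose, a 1-3 h and a 4-7 h sample at each of three visits. Table 3 is thinner: "For the 3 to <7 year-old age range, two sampling timepoints are taken at each visit", one before the dose and one after it. On the post-dose draw, footnote d states: "The post-dose sample may be taken at either collection window A or collection window B". It then asks for variation within a child: "So, an attempt should be made to vary the collection time of the second sample as is feasible". Its one example reads "if on visit 5 the second sample is taken in collection window B, at visit 9 or 16", with window A then suggested for the later draw. The wording is advisory throughout, and actual collection times must be recorded.

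PK visits are Visits 5, 9 and 16 (Weeks 2, 6 and 13; Section 11.5). In Table 4 these weeks fall in the 4, 8 and 12 mg/kg BID periods respectively.

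Section 11.5 plans the descriptive output: "The concentrations will be summarized by time, dose level, and age group". It adds a dose-relationship analysis of trough concentrations, an optional sparse NCA for Cmax and AUCtau, and a population PK model that is refined with the paediatric data and then used to simulate each child's profile. Further PK detail is left to a separate PK SAP, and full sampling detail to a Laboratory Manual. Neither is among the documents.

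**The concern.** With one PK visit per nominal dose, varying the window by visit also means varying it by dose. Footnote d spreads windows within a child. It does nothing to spread them across children at a given dose, which is what a summary by time, dose level and age group needs. If most sites find the same window convenient at the same visit, that dose has no early samples, or no late ones, in the children on Table 3. All of Group 3 (3-5 years) is on that table; in Group 2 only the 6-year-olds are.

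PK is part of the primary objective. The expectation that children will not exceed adult exposure rests on allometric prediction from adults (Section 6.2.1 and Appendix A), and observed concentrations in the smallest children are the direct check on it. The early window has particular value because Section 5.7 places most of the adult drug-related neurological events within 2-3 hours of the first dose.

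**Working it through.** The documents give no precision or sample-size figure for PK sampling, so there is none to reproduce. The sample counts agree with the tables: 3 visits × 3 = 9 samples in Table 2 and 3 × 2 = 6 in Table 3.

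**Inputs.** From the Protocol: three PK visits, one per nominal dose; one post-dose sample per visit under age 7; about 20 completers; at least 3 children per age group (Section 8); 4 to 7 sites (synopsis). The number under 7, n, is not stated. The floor is 3 (the Group 3 minimum). The ceiling is 20 − 3 = 17, reached only if Group 1 is at its minimum and every Group 2 child is 6. I show n = 3, 6 and 9. How sites choose is an assumption.

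**Can window and dose be separated?** Take a model with child, dose and window terms.
- One child: 3 post-dose samples, 1 + 2 + 1 = 4 parameters, rank 3. Not separable.
- Three children with the same sequence: 3 + 2 + 1 = 6 parameters, rank 5. Not separable.
- Two children with different sequences, such as A-B-A and B-A-B: 2 + 2 + 1 = 5 parameters, rank 5. Separable, given additive effects.

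**Chance that at least one dose lacks a window.** If each child has window A with probability p, independently, one visit lacks a window with probability q = pⁿ + (1 − p)ⁿ. With independent choices at the three visits, the chance for at least one dose is 1 − (1 − q)³.
- p = 0.5, n = 3: q = 0.25; 1 − 0.75³ = 0.578.
- p = 0.5, n = 6: q = 0.031; result 0.091. For n = 9: q = 0.004; result 0.012.
- p = 0.8, n = 3: q = 0.512 + 0.008 = 0.52; 1 − 0.48³ = 0.889.
- p = 0.8, n = 6: q = 0.262; 1 − 0.738³ = 0.598. For n = 9: q = 0.134; 1 − 0.866³ = 0.351.

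If every child strictly alternates from a random 50:50 start, the three visits fail together, so the chance for at least one dose is simply q = 2 × 0.5ⁿ.

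| Children under 7 | Free choice, 50:50 | Free choice, 80% prefer one window | Strict alternation, random start |
|---|---|---|---|
| 3 | 58% | 89% | 25% |
| 6 | 9% | 60% | 3% |
| 9 | 1% | 35% | 0.4% |

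If all children share one sequence, the chance is 100% at any n. The same holds if they all use the same window at any single visit. For example, if every site began with B at Visit 5, as in the footnote's example, 4 mg/kg would have no 1-3 h sample under age 7.

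**The case against.** The strongest reply is that footnote d suits the main analysis. The stated route to individual exposure is NCA on profiles simulated from a population model. That model uses actual sampling times and is refined with this trial's own paediatric data, including both windows at every PK visit from ages 7-12. A child under 7 who varies windows supplies the other window at another dose, and adult PK looked linear and roughly dose-proportional (Section 5.7). A pre-dose sample is taken at every visit and also serves as the approximate 12 h point (Table 3, footnote b), so information near the end of the interval is never missing. The trough dose-relationship analysis does not depend on the window. Sparse NCA is optional. The unseen PK SAP or Laboratory Manual might also address balance.

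Most of this stands, and it limits the consequence. A reader might infer that an empty window leaves exposure to be extrapolated from the adult model alone; Section 11.5 does not support that. What survives is that a model filling an empty cell in 3-5-year-olds borrows from older children and adults, and no analysis plan can recover a sample that was not drawn.

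Enrolment is also to be balanced by age as far as possible, so 3 children is a floor rather than an expectation.

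**Conclusion.** An unbalanced dose level in the youngest children is possible, and nothing in these documents prevents it. The risk depends on two unknowns: the number under 7 and how sites choose. It runs from 0.4% (9 children, strict alternation from a random start) to 89% (3 children, 80% preference). The 50:50 and 80% figures are scenarios, not documented behaviour.

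Two stronger readings are tempting but not supported. One is that window is confounded with dose. That is exact within a child, or if every child shares a sequence, but two children with different sequences already break it, and footnote d fixes no sequence. The other is to take 58% or 89% as the expected risk. Both assume the minimum of 3 children and three independent choices, that is, sites disregarding the request to vary.

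The effect is limited to post-dose summaries by time, dose and age group, the optional sparse NCA of Cmax and AUCtau, and how far the population model must borrow. The visit-to-dose mapping is nominal; down-titration or a late DSMC decision would change it. Because PK is a primary objective and the remedy costs little, it is worth making, as a cheap improvement rather than a correction of an error.

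**What to change.** Replace site choice with a central pre-assignment by order of enrolment among children under 7, within age group. Odd-numbered children follow A-B-A and even-numbered children B-A-B at Visits 5, 9 and 16. Allow a deviation when the assigned draw is not feasible, and record the actual time as now.

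This plans both windows at every PK visit from two children on. Planned early-window counts at Visits 5/9/16 are 2/1/2 with 3 children, 3/3/3 with 6 and 5/4/5 with 9. Within-child variation is kept.

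It does not guarantee that no window is empty. With 3 children one window at each visit rests on a single child. If each draw failed independently with an assumed probability of 10%, both windows would be filled at a visit with probability 0.9 × 0.99 = 0.891, so some window would be empty with probability 1 − 0.891³ = 29%. A child whose dose differs from the nominal schedule also disturbs the balance by dose.

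Cost: one line in Table 3 and in the Laboratory Manual, a central list across 4 to 7 sites, and slightly less scheduling freedom. The number of samples and the blood volume do not change.
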